2 INTRODUCTION

2.1 Study Rationale

COVID-19 is caused by the novel SARS-CoV-2 and is associated with a hyper-inflammatory immune response which leads to severe and potentially life-threatening symptoms. Little is known about how and the extent to which COVID-19 presents in people with immunodeficiencies, but because of the known severity of the illness in the general population, vaccination against SARS-CoV-2 is critical. Understanding whether immunodeficient individuals produce an adequate immune response to the COVID-19 vaccine, as well as the number and type of AEs experienced in these people is necessary.

2.2 Background

The novel human coronavirus SARS-CoV-2 is transmitted primarily via respiratory particles and infects the respiratory tract via the receptor angiotensin-converting enzyme 2 (ACE2), which is highly expressed in the respiratory tract as well as on various epithelial tissues throughout the body.¹ This receptor is also used by SARS-CoV, however SARS-CoV-2 has been found to bind to ACE2 with higher affinity than SARS-CoV, potentially increasing the infectivity seen with this virus.² Since the beginning of the pandemic, and as of the writing of this protocol (a period of just over 1 year), SARS-CoV-2 has resulted in over 93 million confirmed infections globally, with over 2 million deaths.³

The disease caused by this virus, COVID-19, has a wide range of clinical manifestations, from completely asymptomatic or mild disease, to severe illness requiring hospitalization, to long-term sequelae (dubbed “long COVID”). Much of the pathology associated with COVID-19 is due to an aggressive immune response which can result in airway damage and acute respiratory distress syndrome (ARDS), among other pathologies.⁴ Unfortunately, there is currently little to no published data on the extent to which COVID-19 is experienced in individuals with immune deficiencies, especially those caused by inborn errors. It is important to know the incidence and clinical presentation of COVID-19 in these individuals to further our understanding of the role immune system activation plays in the development and progression of COVID-19.

Additionally, with the recent emergency use authorizations (EUAs) granted by the US Food and Drug Administration (FDA) for two messenger RNA (mRNA)-based COVID-19 vaccines and subsequent approval of one of these, and with more vaccines in the pipeline, there is a need to understand the post-vaccine immune response in individuals after vaccination to ensure adequate induction and duration of protection. However, individuals with immunodeficiencies are typically excluded from vaccine trials measuring safety and immunogenicity, as was the case for the two COVID-19 vaccines currently authorized or approved. These groups of people must be evaluated to determine the efficacy and tolerability of vaccines, especially in light of concerning anaphylaxis episodes in a minority of people who were vaccinated against COVID-19.⁸

There is some literature regarding the immune response in individuals with inborn errors of immunity to vaccination, including inactivated or subcomponent vaccines like the influenza or *Haemophilus influenzae* type b vaccines,^{5,6} and live-attenuated vaccines such as the measles-mumps-rubella and varicella vaccines.⁷ Depending on the immunologic defect, vaccine immunogenicity can vary widely, leaving some immunodeficient individuals inadequately protected. For example, individuals with complement defects should produce B- and T-cells in levels relatively similar to that of healthy volunteers, while others, like those with Wiskott-

Aldrich Syndrome, produce antibodies but a weak or absent T-cell response, and those with common variable immunodeficiency are only capable of producing T-cells without antibody. Because of this complexity, it is necessary to obtain a comprehensive understanding of the immunologic response to vaccines to better understand both the level of cellular and humoral protection against COVID-19 and also their estimated contribution to herd immunity.

Unfortunately, individuals with immunodeficiencies are typically excluded from vaccine trials measuring immunogenicity and safety, as was the case for the COVID-19 vaccines currently authorized or approved for use in the United States. This creates a need to study AEs in immunodeficient people to determine the safety and tolerability of the COVID-19 vaccines, especially in light of concerning anaphylaxis episodes in a minority of people who were vaccinated against COVID-19,⁸ even though AEs in this group, specifically in individuals with impaired T-cell responses, are usually limited to live vaccines.

The aims of this study are to characterize the immune response to COVID-19 vaccination, the number and type of vaccine-associated AEs, and pre- and post-vaccine COVID-19 disease prevalence and severity in individuals with different types of immune defects. Potential diseases of interest that are followed at NIAID include those with neutrophil dysfunction such as chronic granulomatous disease and leukocyte adhesion deficiency; combined immune deficiencies such as DOCK8 (dedicator of cytokinesis 8) deficiency, leaky severe combined immunodeficiencies (SCIDs; e.g. RAG (recombination-activating gene) deficiency), X-linked immunodeficiency with magnesium defect, Epstein-Barr virus infection, and neoplasia (XMEN) disease (T-cell deficiency), STAT3 (signal transducer and activator of transcription 3) deficiency (Hyper IgE syndrome), defects of the PI3K (phosphoinositide 3-kinase) pathway; predominantly B lymphocyte defects such as X-linked agammaglobulinemia and common variable immune deficiency (CVID); defects of the Interleukin 12 (IL-12)/Interferon gamma (IFNg)/STAT1 pathway; *GATA2* deficiency; and those with immune activation such as neonatal-onset multisystem inflammatory disease (increased inflammasome activity) and autoimmune polyendocrinopathy-candidiasis-ectodermal dystrophy (APECED).

2.3 Risk/Benefit Assessment

2.3.1 Known Potential Risks

Blood collection: The risks of venous blood draws include pain, bruising, bleeding, fainting, and, rarely, infection. The risk of finger sticks include minor, transient pain.

Saliva collection: There are no risks associated with collection of saliva by expectoration.

Questionnaire completion: There is a minimal risk of loss of confidentiality of information collected in the questionnaires.

2.3.2 Known Potential Benefits

Participants will not receive direct benefit by participating in this study. The information learned in this study may improve the investigators' understanding of the immune response and AE profile in individuals with immune deficiencies to COVID-19 vaccination, as well as the severity of COVID-19 in these individuals, which may have implications for individual care and further prevention of COVID-19. Such information may also be useful in designing more effective vaccines to prevent the spread of SARS-CoV-2, which may benefit others in the future.

2.3.3 Assessment of Potential Risks and Benefits

COVID-19 is a global pandemic with few approved treatments and a wide range of disease presentations and outcomes. Better characterization of disease presentation and immune response in individuals with immune dysfunction, which is the objective of this study, may contribute to the knowledge of how the immune system responds to COVID-19 vaccination and how it contributes to COVID-19 disease development. While study participants will be exposed to some risk from blood draws, those risks are outweighed by the benefits to generalizable knowledge.

3 OBJECTIVES AND ENDPOINTS

Objectives	Endpoints	Justification for endpoints
Primary		
To characterize the immune response to COVID-19 vaccination among immunodeficient and immune dysregulated individuals compared to healthy volunteers.	Change in S and RBD IgG antibody titer from baseline to 14-21 days or 21-28 days (depending on vaccine manufacturer and platform) after dose 1, and 21-28 days after dose 2 and any subsequent doses (depending on vaccine manufacturer and platform).	It is of interest to understand the changes in anti-SARS-CoV-2 antibody levels induced by vaccination in individuals with immune deficiency/dysregulation.
Secondary		
To characterize the COVID-19 vaccine-associated AEs among immunodeficient and immune dysregulated individuals compared to healthy volunteers.	Incidence of vaccine-associated AEs experienced by immunodeficient and immune dysregulated individuals compared to healthy volunteers.	It is of interest to understand the safety (by knowing the incidence of AEs) of COVID-19 vaccines in individuals with immune deficiency/dysregulation.
Exploratory		
Assess the relationship between prior SARS-CoV-2 infection and vaccine-induced immune response.	Characterization of post-vaccine immune response and AEs in patients with antibody evidence of prior SARS-CoV-2 infection compared to those without evidence of prior infection.	Because so many people have had SARS-CoV-2 infections prior to vaccination, it is of interest to understand whether this affects the immune response to vaccination.

To characterize pre-vaccine COVID-19 disease prevalence and severity among immunodeficient and immune dysregulated individuals.	Incidence of COVID-19-and associated symptoms experienced in individuals with immune deficiency/dysregulation who are positive for SARS-CoV-2 by serology or diagnostic PCR.	It is of interest to understand the incidence and clinical presentation of COVID-19 in individuals with immune deficiency/dysregulation, especially as COVID-19 is an inflammatory-mediated disease.
To assess induction, strength, and durability of T- and B-cell-specific immune responses to SARS-CoV-2 (as measured by frequency and diversity of SARS-CoV-2 specific T and B cell clonotypes and titers of specific antibody responses), and their correlation to the underlying immune deficiency/dysregulation.	Characterization how various forms of immunodeficiency impact generation, strength, and durability of T- and B-cell responses.	It is of interest to have a detailed understanding of the immune response to COVID-19 vaccination in individuals with immune deficiency/dysregulation.
To characterize autoantibodies present in immunodeficient and immune dysregulated individuals before and after COVID-19 vaccination.	Incidence of autoantibodies pre- and post-COVID-19 vaccination comparing individuals with immune deficiency/dysregulation to healthy volunteers.	Autoantibodies are effectors of immune response and can influence the efficacy of vaccination.
To assess the incidence and genetic sequence of post-vaccination SARS-CoV-2 infection.	Incidence and genetic sequence of post-vaccination SARS-CoV-2 infection as reported by patient and confirmed by PCR and sequencing.	With the rise in genetic variants of SARS-CoV-2, it is important to understand how many vaccinated individuals are still susceptible to infection.

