Participants who are able to come to the NIH will have the additional option to provide blood samples at days 1 and 3 after each vaccination in order to capture immediate vaccine-induced perturbations of immune responses. Samples will be used to study short-term immunological effects of immunization and boosting. If additional booster doses are received, participants will be asked to submit optional blood samples 21-28 days after the booster vaccination(s), through the 5th dose of a COVID-19 vaccine. Samples received outside of that window samples received outside of the requested windows are acceptable and will be analyzed at the discretion of the PI. Additional optional blood samples may be provided at approximately 6, 12, and 24 months after the final vaccination to assess long-term immunological persistence of vaccine-derived antibodies and T-cell responses. Research evaluations on these samples will include baseline and post-vaccine autoantibody levels as well as SARS-CoV-2 antibody titers to the S, N, and RBD proteins. Serology has been validated across fresh serum and dried blood samples collected using microsamplers (see Figure below)⁸. Venous blood draw may be waived if a participant is unable to obtain it at any given timepoint.

[figure not shown]

Figure 1. Quantification of antibody concentration utilizing 4PL sigmoidal model of recombinant antibody spiked into seronegative blood. **A)** Anti-RBD recombinant human antibody (IgG and IgM) was added to whole blood from two seronegative donors, then absorbed to microsamplers and remaining blood was spun down to isolate serum and analyzed on full spike ectodomain trimer (spike) or receptor-binding domain (RBD) ELISA. Data are mean \pm SEM, n = 3, red = microsampler eluate, gray = matched serum. **B)** Direct comparison of absorbance of range of recombinant antibody concentration in serum (y axis) versus microsampler (x axis) blood samples. **C)** Sigmoidal four-parameter logistic (4PL) curve fitting to recombinant antibody dilution series, 95% confidence intervals shown shaded around fit curve, n = 12 replicates per data point, red = Spike IgG, orange = RBD IgG, blue = Spike IgM, purple = RBD IgM. **D)** Quantification of IgG levels in a sample high-incidence population. **E)** Upper limit of quantification at 1:400 dilution of serum into ELISA (1:10 dilution of microsampler eluate), n = 68. From ref⁸

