5.2 Exclusion Criteria

Individuals meeting any of the following criteria will be excluded from study participation:

1. Receipt of any other vaccine within 14 days prior to screening.
2. Planned non-COVID-19 vaccination within 28 days after COVID-19 vaccination(s).
3. Any condition that, in the opinion of the investigator, contraindicates participation in this study (e.g. specific autoinflammatory diseases, interferonopathies).
4. Self-reported history of HIV.

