Electronic questionnaires: Five separate Research Electronic Data Capture system (REDCap) questionnaires will be completed electronically in REDCap by subjects and/or their parents/guardians throughout the study. A link to the questionnaires will be sent to the personal email address on file. The baseline questionnaire will capture medical history, and any COVID-19 symptoms, severity, and treatment the participant may have experienced. The follow-up questionnaires will assess changes in health history or medications and AEs following study vaccination. An optional survey will ask participants about their beliefs and behaviors around COVID-19 vaccinations, and whether they have changed since before the primary vaccine series and/or booster doses. The questionnaires and their timing are listed below:

1. Baseline medical history and screening questionnaire (Baseline)
2. COVID-19 baseline/post-vaccine infection symptom questionnaire (Baseline and following COVID-19 infection)
3. Changes in medical history questionnaire (Following sample collection)
4. Post-vaccine adverse events questionnaire (Following vaccination)

5. COVID-19 Attitudes and Behaviors Survey (Following primary series and/or booster)

AE assessment: Only AEs related to study procedures (blood draw, fingerstick, and saliva collection) will be followed. COVID-19 vaccines are not administered as study procedures under this protocol; therefore, while we are interested in collecting AEs related to vaccination in our study population, these are not considered study-related events and will not be followed as such. Subjects will be assessed for AEs at each study visit. Information on AEs related to the study procedures that develop within 2 days after the procedure will be collected by participant report and followed through resolution or until the site investigator judges that the event has stabilized and no additional follow-up is required.

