8.3 Sample Size Justification

The sample sizes proposed in this protocol were set based on the primary objectives of this study, which are to characterize the immune response to COVID-19 vaccination as measured by enzyme-linked immunosorbent assay (ELISA) anti-S-2P and anti-RBD IgG titers at approximately 3-4 weeks following each vaccination and in long-term follow-up. The following sample size determination is based on results of the phase 1 dose escalation study of the Moderna mRNA vaccine.⁹ Fifteen participants received a dose of 100 ug of vaccine, and the means and standard errors of the log₁₀ antibody titers at the nearest timepoints to the times at which we propose to collect samples are summarized in the table below.

Target	Study day	Mean log ₁₀ -titer (Standard error)
S-2P	29	5.04 (0.28)
	56	5.89 (0.19)
RBD	29	4.97 (0.38)
	56	5.57 (0.27)

We assume that healthy volunteers in the upcoming trial have similar immune responses to those reported in the Moderna Phase I trial, and that immune deficiency/dysregulation shifts the log₁₀-titer distribution among individuals with immune deficiency/dysregulation but does not change the standard deviation of the responses. We also suppose that healthy volunteers and immune deficient/dysregulated individuals have similar baseline distributions, which is reasonable as both groups are naïve at baseline. As we were unable to obtain specific estimates of antibody responses to the Pfizer vaccine that could be used to estimate the sample size for this study, we are left to assume that responses to the Pfizer vaccine are similar to the Moderna vaccine.

Using the estimates from the Moderna study, we calculate, and plot below, the smallest differences in mean log-titers that we would be able to detect using a two-sided two-sample t-test with either 80% or 90% power while controlling the type I error rate at $\alpha=0.05$ as a function of sample size. We also display the widths of 95% confidence intervals for a difference in mean log-titers. As an example, a sample size of 20 immune deficient/dysregulated individuals and 20

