8.4.1 Analysis of the Primary Endpoint

Log transformed antibody measurements will be modeled within a mixed model repeated measures (MMRM) framework, which is a longitudinal mixed model with fixed effects for (categorical) timepoint, immune deficiency/dysregulation, and the interactions of timepoint with immune deficiency/dysregulation and timepoint with baseline measurement, along with possible adjustment other covariates, such as age and sex. In this framework, we also include correlated subject-level random effects for each timepoint to account for clustered data. This also allows us to estimate the correlation between antibody responses to the first and second doses of vaccine. MMRM models are an appropriate tool for assessing response profiles in longitudinal studies where missing data is expected and it is appropriate to assume that data are missing at random conditional on observable covariates.^{13,14} The previous sample size justifications based on two-sample t-tests are likely to be slightly conservative as we expect the MMRM framework to make more efficient use of the data. Models will either be fit using the 'nlme' package in R, or, if a Bayesian formulation is deemed to be preferable for the purpose of incorporating prior information, can be fit using the 'brms' and 'rstanarm' packages.

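### No rule separates S/RBD IgG received as treatment from IgG made after vaccination, so the primary patient-versus-healthy contrast can be biased in either direction

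*Combined protocol and SAP*

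**What the plan says.** - **Endpoint.** Section 3 gives the primary endpoint as "Change in S and RBD IgG antibody titer from baseline to 14-21 days or 21-28 days" after dose 1, then 21-28 days after dose 2 and later doses. Its stated interest is "changes in anti-SARS-CoV-2 antibody levels induced by vaccination in individuals with immune deficiency/dysregulation".
- **Analysis.** Section 8.4.1: "Log transformed antibody measurements will be modeled within a mixed model repeated measures (MMRM) framework". The fixed effects are timepoint, immune group, timepoint by group and timepoint by baseline; age, sex and other covariates are optional. Section 8.4 adds an analysis adjusted for SARS-CoV-2 infection, the only planned allowance for another source of antibody.
- **Baseline.** Section 8.3 supposes that "healthy volunteers and immune deficient/dysregulated individuals have similar baseline distributions", on the ground that everyone is naive.
- **Eligibility.** The only product-related exclusions in section 5.2 concern other vaccines, for example "Receipt of any other vaccine within 14 days prior to screening". The withdrawal reasons in section 6.1 do not mention antibody products.
- **Data collected.** Section 7.2: "The follow-up questionnaires will assess changes in health history or medications and AEs following study vaccination". The baseline questionnaire also asks about COVID-19 treatment. No analysis rule uses either item.
- **Population.** Section 8.2 plans 40 antibody-deficient and 50 combined-deficiency patients, plus transplant and gene-therapy groups. Section 8.3 names XLA and CVID. Section 2.2 says that "those with common variable immunodeficiency are only capable of producing T-cells without antibody". Under section 5.1, controls must have no evidence of immune deficiency.
- **Assay.** In the validation experiment of section 4.1 (Figure 1 legend), "Anti-RBD recombinant human antibody (IgG and IgM) was added to whole blood from two seronegative donors" and the result was quantified.

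**The concern.** The endpoint is meant to show what the vaccine induced, but it measures all S/RBD IgG in the sample. The validation experiment shows that the assay reads antibody the donor did not make. Nothing in the plan prevents a value that comes wholly or partly from a treatment product from entering the model as vaccine response.

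The problem is unlikely to cancel between arms. Controls have no immune deficiency by definition, so immunoglobulin replacement should fall almost entirely among patients. Those include the two groups for which section 8.3 expects poor antibody responses and relies on resolving a difference from controls. The mean IgG contrast there could be distorted by treatment exposure. The dose 1 to dose 2 correlation (section 8.1) and the exploratory durability objective would share the problem. The exploratory analysis by antibody evidence of prior infection, and the infection-adjusted analysis if infection is defined by serology, could misclassify recipients.

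**Working it through.** **Inputs from the documents (section 8.3).** Anti-RBD at day 29: mean 4.97, spread 0.38 log10. The table calls 0.38 a standard error, but the plan's own figures require it to be a standard deviation, so it is used as one here. Two-sided two-sample t-test, alpha 0.05, 20 per group. Healthy volunteers number 100 in the synopsis and 120 in section 8.2; 100 is used below.

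**Inputs not in the documents (assumed).** The share f of a patient group exposed to given antibody, and how much that antibody adds to the reading. Both are shown over a range.

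**Step 1: reproduce the plan's figures.** Noncentrality = difference / (SD × √(1/n1 + 1/n2)), with 0.38 × √(2/20) = 0.120.
- 0.40/0.120 = 3.33 on 38 df: power 0.900 (plan: 90%).
- 0.35/0.120 = 2.91: power 0.810 (plan: 80%).
- 1.05 SD: power 0.899 (plan: 90%).

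**Step 2: direction of the bias.** Illustrative scale: baseline floor 1 unit, V units made after vaccination, P units given.
- Given after baseline: change = log10(1 + V + P). With V = 0, P = 10 gives log10(11) = 1.04 and P = 100 gives log10(101) = 2.00. Both are false rises.
- Present and stable from baseline: change = log10[(1 + P + V)/(1 + P)]. With V = 100 and P = 10 this is log10(111/11) = 1.00, against log10(101) = 2.00 without P. A true rise is understated.
- Cross-sectional comparison (section 8.1, second hypothesis): given antibody still present in the sample raises the level.
- Enrollees after vaccination with no stored baseline (section 4.1): only the post-vaccination level is available, so the effect is again upward wherever their values are used.

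**Step 3: what the baseline term does.** Timepoint by baseline fits one slope per timepoint across all groups. The same baseline value may reflect past infection in one person and donor IgG in another, with different implications for the later value. One common slope corrects for this only in part.

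**Step 4: size under one simple mixture.** Suppose a share f of patients reads at the healthy level because of given antibody, and the SD is unchanged. Observed deficit = d(1 − f). With d = 0.4:

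| f (assumed) | Observed deficit | Power, 20 vs 20 | Power, 40 vs 100 |
|---|---|---|---|
| 0 | 0.40 | 0.90 | >0.99 |
| 10% | 0.36 | 0.83 | >0.99 |
| 25% | 0.30 | 0.68 | 0.99 |
| 50% | 0.20 | 0.37 | 0.80 |
| 75% | 0.10 | 0.12 | 0.29 |

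More participants restore power but leave the estimate wrong: a true deficit of 1.0 still reads as 0.75 at f = 25% and 0.50 at f = 50%.

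**Step 5: power if exposed participants are set aside** (difference of one SD, the target in section 8.3):

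| f (assumed) | 20 vs 20 | 20 vs 100 | 40 vs 100 |
|---|---|---|---|
| 0 | 0.87 | 0.98 | >0.99 |
| 25% | 0.81 | 0.95 | >0.99 |
| 50% | 0.70 | 0.85 | 0.98 |
| 75% | 0.48 | 0.58 | 0.85 |

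**The case against.** The documents do not mention any of the three products. That they are allowed, and that their IgG would be counted, follows from silence; that they are used in these diseases is general knowledge. For monoclonal antibody and plasma nothing shows use by arm, and a control treated for COVID-19 could receive either. The study describes itself as exploratory, its covariate list is open, medication data are collected, and IgM, IgA and clonotype data are planned. The questionnaires and Manual of Procedures are not in the file and may already record exposure. All of this stands and limits how firmly the point can be put. It does not supply an analysis rule.

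Three stronger readings are tempting, and the documents support none of them.

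- **A non-responder would be scored as a responder.** There is no responder definition or threshold; the endpoint is a continuous change in log titer.
- **The bias always favours an adequate response.** Someone on continuing replacement carries donor IgG at baseline as well, and Step 2 shows that the log change is then understated.
- **Given antibody would erase a one-SD deficit.** A reader might take 20% exposed and a 2.0 log10 rise, so 0.2 × 2.0 = 0.40 against 0.38. Both inputs are invented. Section 8.3 sets the one-SD target for groups without prior information, not for those expected to respond poorly. Under its shift model with unchanged SD, a group one SD down averages 4.97 − 0.38 = 4.59; adding 2.0 puts recipients near 6.59, above even the healthy day-56 RBD mean of 5.57.

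**Conclusion.** The gap is real and affects the primary comparison: run as written, section 8.4.1 would treat given IgG as vaccine-induced IgG. The direction depends on timing. It is upward for antibody first received after baseline, for post-vaccination enrollees without a baseline, and for cross-sectional levels; it is downward for the log change when donor IgG is stable from baseline.

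The size cannot be derived from the documents. The fall from 0.4 to 0.30 or 0.20 log10 rests on an assumed exposure share of 25% or 50% and on exposed patients reading at the healthy level. The imbalance between arms is a reasonable inference for immunoglobulin replacement and unknown for the other two products. Exposure dates may be hard to recover later, and without them the analysis cannot tell which samples are affected.

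**What to change.** 1. Add product and last-administration date to the existing medication questionnaires (section 7.2).
2. In section 8.4.1, define receipt of an antibody product as an intercurrent event. After a monoclonal antibody or convalescent plasma, do not use S/RBD IgG as vaccine response for a prespecified, product-specific period. The documents give no such period, so the sponsor must set and justify it. Because receipt may depend on poor response, add a sensitivity analysis to the missing-at-random assumption.
3. Report the IgG contrast separately for immunoglobulin-replacement recipients and non-recipients. Use S/RBD IgM and IgA, which the section 1.2 schedule lists for the same microsample, as supportive measures. Use T-cell data only where venous samples exist: microsampler-only participants are tested for SARS-CoV-2 antibodies and autoantibodies alone, and PBMC tubes may not be drawn at every visit.
4. Do not classify recipients as previously infected on IgG serology alone.

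The cost is extra questionnaire fields and analysis-plan text, fewer usable IgG values, and a split in the antibody-deficient groups. Step 5 shows that a group of 40 against 100 controls can absorb this. Groups of about 20 or fewer lose power if most members are exposed: 0.58 for one SD against 100 controls at 75%. Nobody's treatment changes.
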